5.5.1.2. Analyses by Serotype

Analyses by serotype to evaluate the prophylactic efficacy against DENV infection and against symptomatic DENV infection will be done upon the condition that at least 6 cases of the same serotype are observed over the JNJ-64281802 and placebo in group that will be compared.

In this analysis, a laboratory confirmed DENV infection is defined through the detection of DENV RNA of a specific serotype between baseline and the last day of dosing + 1 day. Infections with other serotypes will be excluded from this analysis.

The same significance level, attributes and analysis methods as for the primary and key secondary endpoint will be used (see sections 5.3 and 5.4.1).

No sensitivity or subgroup analyses will be done for these analyses.

5.5.1.3. Quantitative DENV RNA VL Levels

Descriptive analyses will be done to evaluate

- the prophylactic effect of JNJ-64281802 with respect to reduction of DENV RNA among enrolled HHC who have no evidence of current DENV infection at baseline and who are infected post baseline
- the antiviral effect of JNJ 64281802 as early treatment among HHC who have evidence of DENV infection at baseline.

Data Handling Rules

Serum DENV RT-qPCR levels will be assessed using a validated quantitative DENV RT - qPCR assay.

Measurements collected from screening visit to the end of study below the lower limit of detection (LOD) and below/above the lower/upper limit of quantification (LLOQ/ULOQ) for each of the 4 serotypes on this assay will be handled according to the rules summarized in Table 5.

Table 5: Data Handling Rules for DENV RT-qPCR levels (copies/mL)

				Imputed Values		
				target not	<lloq target<="" th="">	</lloq>	
Serotype	LOD	LLOQ	ULOQ	detected ⁽¹⁾	detected ⁽²⁾	>ULOQ ⁽³⁾
DENV-1	29	1000	1 000 000 000	15	500	1 100 000 000
DENV-2	60	1000	1 000 000 000	15	500	1 100 000 000
DENV-3	36	1000	1 000 000 000	15	500	1 100 000 000
DENV-4	55	1000	1 000 000 000	15	500	1 100 000 000

⁽¹⁾ LOD (from DENV-1)/2 rounded to the nearest integer

Before any other rule is applied, the value for each day is defined as the maximum value of assessments performed on that day for each assay (DENV-1, DENV-2, DENV-3 and DENV-4). This is applied for each day separately.

Endpoint Definitions

Measurement	Formula/Definition	
Reduction of DENV RNA among HHC who have no evidence of current DENV infection at baseline and who are infected post baseline		
Peak of detectable DENV RNA	Maximum of all measured DENV RNA values	
	as early treatment among HHC who have evidence of	
current DENV infection at baseline		
Peak of post baseline detectable DENV RNA	Maximum of all post-baseline measured DENV RNA values	
Time to end of detectable DENV RNA	Minimum of (days with undetectable DENV RNA after the last detectable DENV RNA result) – Day 1 + 1	
	If the last measured DENV RNA result is still detectable, the value will be censored at the last available sample.	

⁽²⁾ LLOQ/2

⁽³⁾ ULOQ+(ULOQ/10)

Analysis Methods

Reduction of DENV RNA among HHC who have no evidence of current DENV infection at baseline and who are infected post baseline:

Descriptive statistics on peak of detectable DENV RNA will be calculated for each study intervention group separately. Statistics include sample size (n), mean, SD, median, minimum, and maximum.

Antiviral effect as early treatment among HHC who have evidence of current DENV infection at baseline:

Descriptive statistics on peak of post-baseline detectable DENV RNA will be calculated for each study intervention group separately. Statistics include sample size (n), mean, SD, median, minimum, and maximum.

Time-to end of detectable DENV RNA will be analyzed using Kaplan-Meier (KM) estimates. A summary table including number of participants included in the analysis, number of participants censored, 25th and 75th percentiles, and median time-to-event, with 95% CIs based on log-log transformation method, will be presented. The data will be presented graphically using the Kaplan-Meier estimate of the survival function by study drug.

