2. INTRODUCTION

Dengue is caused by any of the 4 antigenically distinct dengue virus (DENV) serotypes (DENV-1, -2, -3, and -4), which belong to the genus *Flavivirus* in the family of the *Flaviviridae*. The DENVs are human pathogens which are transmitted through the bite of an infected female mosquito of the genus *Aedes*, mainly of the species *Aedes aegypti* and to a lesser extent *Aedes albopictus* (Carrington 2014). Dengue is endemic in more than 125 countries, and it has also again become endemic in the United States of America (USA) and its territories of American Samoa, Puerto Rico, and the US Virgin Islands (CDC 2019a). About half of the global population is currently at risk of becoming infected with DENV, ranking dengue among the top 10 threats to global health in 2019 (WHO 2019a,b).

The actual numbers of dengue cases are underreported, and many cases are misclassified as other febrile illnesses such as malaria. It is estimated that there are 390 million DENV infections globally per year, of which 96 million manifest clinically (with any severity of the disease) (Bhatt 2013). On average, each year about 500,000 dengue cases require hospitalization due to severe and life-threatening diseases and up to 25,000 patients die due to dengue.

During a DENV infection, 1 in 4 infections are symptomatic and 1 in 20 cases develop severe dengue (CDC 2019b) Those that show clinical symptoms mainly develop an acute, self-limiting febrile illness. The first clinical symptoms occur 3 to 8 days after a bite by a DENV-infected and viremic mosquito. Resolution of infection usually occurs within 4 to 7 days due to a robust innate and adaptive immune response (Whitehorn 2011). However, less than 1% of DENV infections result in severe dengue outcomes such as dengue hemorrhagic fever (DHF) and dengue shock syndrome (DSS).

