8.4. Pharmacokinetics

Venous blood samples will be used to evaluate the PK of JNJ-64281802. Plasma collected for PK may additionally be used to evaluate safety or antiviral activity aspects that address concerns arising during or after the study period. Samples may also be used for the analysis of metabolites of JNJ-64281802 or endogenous markers for enzymes or transporters involved in the metabolism and distribution of JNJ-64281802, at the discretion of the sponsor. Genetic analyses will not be performed on these samples. Participant confidentiality will be maintained.

See also Section 8.9, Pharmacokinetic Substudy.

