AE = adverse event; DENV = dengue virus; ECG = electrocardiogram; HHC=household contact; RNA=ribonucleic acid; NS = non-structural protein; PCR = polymerase chain reaction; SAE = serious adverse event.

- ^a DENV infection is defined as a positive DENV RNA or DENV NS1 protein test result.
- Laboratory-confirmed symptomatic DENV infection is defined as having at least 2 solicited systemic AEs (see Safety Evaluations section), of which at least one is a most common dengue symptom (ie, fever, headache/retro-orbital pain, myalgia, arthralgia, rash), lasting for ≥1 day and occurring within a +/-2 days time window around the positive PCR or NS1 test.

The statistical analysis for the following exploratory objectives might be performed, but will depend on the unblinded results of the primary and secondary endpoints, for hypothesis generating purposes:

Objectives	Endpoints
Exploratory	
To evaluate the prophylactic effect of JNJ-64281802 with respect to reduction of DENV RNA among enrolled HHCs who have no evidence of current DENV infection at baseline and who are infected post baseline.	• The maximum DENV RNA levels between baseline and the last day of dosing + 1 day.
To evaluate the antiviral effect of JNJ-64281802 as early treatment among HHCs who have evidence of DENV infection at baseline.	 Time to end of detectable DENV RNA and/or reduction in DENV RNA load. DENV-associated signs and symptoms.

HYPOTHESIS

See Section 2, Statistical Hypotheses.

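### SAP 5.5.1.3 keeps reduction in RNA load as an early-treatment endpoint but defines none, leaves baseline RNA unused, and treats clearance seen on a roughly 4-day grid as exact

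*SAP*

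**What the plan says.** SAP 1.1 lists, for contacts with evidence of infection at baseline, the endpoint "Time to end of detectable DENV RNA and/or reduction in DENV RNA load", with dengue signs and symptoms as a second endpoint. Both are conditional: "The statistical analysis for the following exploratory objectives might be performed, but will depend on the unblinded results of the primary and secondary endpoints". The stated purpose is to generate hypotheses. SAP Appendix 2 (6.2) names the exploratory analyses that are left out, and this one is not among them.

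For this group SAP 5.5.1.3 defines two RNA measures:

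- **Peak:** "Maximum of all post-baseline measured DENV RNA values". On its analysis: "Descriptive statistics on peak of post-baseline detectable DENV RNA will be calculated for each study intervention group separately", meaning n, mean, SD, median, minimum and maximum. Baseline is not mentioned, and Table 5 is in copies/mL with no log transformation stated.
- **Time to end of detectable RNA:** "Minimum of (days with undetectable DENV RNA after the last detectable DENV RNA result"), minus Day 1, plus 1, censored at the last sample if RNA is still detectable. "Time-to end of detectable DENV RNA will be analyzed using Kaplan-Meier (KM) estimates", with median, quartiles and a plot by arm.

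The Schedule of Activities (Protocol 1.3.2.2 and 1.3.2.3) takes viral load predose on Day 1, then on Days 5, 9, 13, 17, 21, 25 and 28 (each ±1 day) during dosing. Samples are to be no more than 4 days apart. The data handling rules in SAP 5.5.1.3 cover values from screening onward, so a baseline level exists.

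**The concern.** A reduction needs a starting value. For contacts who become infected after baseline, a maximum is a natural measure: they start undetectable, and the maximum is the endpoint SAP 1.1 states for them. SAP 5.5.1.3 uses the same kind of measure for contacts who start treatment while already viraemic, where the stated endpoint is a reduction. They enter at unknown and differing points of the infection, so much of the spread in their post-baseline peak reflects how high RNA stood on Day 1. That value is measured and then not used.

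The time measure loses information differently. Clearance happens somewhere between the last detectable and the next undetectable sample, but Kaplan-Meier on the sample day treats it as observed on that day. The Protocol introduction says "Resolution of infection usually occurs within 4 to 7 days due to a robust innate and adaptive immune response". If RNA detectability lasted about that long, a grid with steps of about 4 days would reduce nearly all clearance times to two visits.

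At stake is how an exploratory result is read. Noisy peaks and equal medians could be taken as a sign of no early-treatment effect when the data are only summarised inefficiently.

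**Working it through.** **1. Size of the group.** The plan gives no sample size for this objective, only expected recruitment of 1250, 1455 or 1850 (SAP 3). Inputs from SAP 3: 24 symptomatic events, 1:1:1 allocation, 20% unevaluable, 20% infected at baseline, 7.5% incidence, symptomatic shares 20% (incident) and 10% (prevalent), and efficacy against symptomatic infection of 72.5% for the high dose.

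N = 24 × 3 / [0.8 × (0.8 × 0.075 × 0.20 + 0.2 × 0.10) × (1 + 0.275 + (1 − PE_LDR))] = 72 / [0.0256 × (2.275 − PE_LDR)]

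- PE_LDR 0: 1236 (plan 1250)
- PE_LDR 0.3625: 1471 (plan 1455)
- PE_LDR 0.725: 1815 (plan 1850)

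All are within 2%. The 36-infection target gives 1000, 1200 and 1500, so the symptomatic target governs. Planned numbers infected at baseline: 0.2 × 1250 = 250 to 0.2 × 1850 = 370; evaluable (× 0.8) 200 to 296; per arm about 67 to 99. The trial stopped early and the number actually reached is not given, so 30 per arm is also shown.

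**2. The time measure on the sampling grid.** Gaps from Day 1 to Day 28 are 4, 4, 4, 4, 4, 4 and 3 days. *Assumption:* RNA is detectable for D days, D uniform on 4 to 7. The Day 5 visit falls 4 days after Day 1, and the drug shortens the remaining time by s days.

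- *Entry at a random point of the course (longer courses more likely to be caught):* P(undetectable at Day 5) = E[min(4 + s, D)] / E[D], with E[D] = 5.5. For s = 0: 4/5.5 = 0.73. For s = 1: 4.83/5.5 = 0.88. For s = 2: 5.33/5.5 = 0.97.
- *Whole course after baseline:* P(D ≤ 4 + s) = s/3 = 0, 0.33, 0.67.

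| Scenario | s | Share undetectable at Day 5 | 25th pct | Median | 75th pct |
|---|---|---|---|---|---|
| Random entry | 0 | 0.73 | 5 | 5 | 9 |
| Random entry | 1 | 0.88 | 5 | 5 | 5 |
| Random entry | 2 | 0.97 | 5 | 5 | 5 |
| Whole course ahead | 0 | 0 | 9 | 9 | 9 |
| Whole course ahead | 1 | 0.33 | 5 | 9 | 9 |
| Whole course ahead | 2 | 0.67 | 5 | 5 | 9 |

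The median does not move in three of the four comparisons with s = 0. In the fourth it moves 4 days for a true shift of 2. A quartile moves in all four. With fixed D and random entry the untreated share is 4/D, from 4/7 = 57% to 100%. The ±1 day window blurs the values to Days 4-6 and 8-10.

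**3. What baseline adds.** *Assumptions (no kinetics in the documents):* baseline 3 to 8 log10 copies/mL; decline from Day 1 of 0.7 or 1.0 log10 per day (SD 0.2), 1.3 times faster on drug; measurement SD 0.3; nominal visit days; two-sided 5%, two arms, 500 runs each. The unadjusted peak and the time were compared by rank test, the adjusted peak by a linear model with baseline log10 RNA. Each pair is for decline 0.7 and 1.0.

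| Measure | 30 per arm | 67 per arm |
|---|---|---|
| Unadjusted peak | 0.33, 0.54 | 0.68, 0.85 |
| Time on Day 5/9/13 grid | 0.36, 0.46 | 0.73, 0.79 |
| Peak minus baseline | 0.61, 0.46 | 0.92, 0.80 |
| Peak adjusted for baseline | 0.69, 0.85 | 0.97, 0.99 |

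With no effect, every measure rejects in 0.03 to 0.08 of runs. The plain difference gains at the slower decline but not at the faster one, plausibly because values reach the detection floor. Adjustment gains in both.

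**4. Scale.** Table 5 imputes from 15 to 1,100,000,000 copies/mL. One participant above the upper limit adds 1,100,000,000/30 ≈ 37 million to the raw mean of an arm of 30.

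**The case against.** A reader might infer that the planned outputs cannot show an early-treatment effect, or that a false finding of no effect is likely. The documents do not support that, for these reasons:

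- Arms are randomised, so stage of infection at entry is balanced in expectation. Ignoring baseline costs precision and leaves chance imbalance uncorrected, but the contrast is valid.
- The endpoint is worded with and/or, so clearance time alone can answer it. SAP 5.5.1.4 also analyses signs and symptoms for the same objective.
- Quartiles and Kaplan-Meier curves are pre-specified, and step 2 shows they can move where the median does not. The random-entry shift is fragile, because 0.73 lies just under 0.75.
- The SAP formula uses days, and visits have a ±1 day window, so times are not confined to 5, 9 and 13.
- The 4-to-7-day statement follows text on symptomatic febrile illness. It is not a duration of RT-qPCR detectability in asymptomatic contacts.
- The analysis is descriptive and conditional, with no test or decision rule.

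All of this stands. It removes the strong reading and lowers the severity. It does not supply the missing definition of reduction or explain why the Day 1 value goes unused.

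A reader might also want an earlier RNA value from the Day 3 PK draw, since Protocol 8.4 says "Plasma collected for PK may additionally be used to evaluate safety or antiviral activity aspects". That sentence goes on to limit the use to concerns arising during or after the study. The planned RNA assay is on serum, and the trial ended on 02 October 2024, before the SAP was approved on 21 October 2024. That proposal is not made here.

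**Conclusion.** The point holds as a gap in definition and a loss of precision. A retained endpoint has no defined measure of reduction, the peak ignores a baseline that was collected, and interval-censored clearance is treated as exact. Under the assumed kinetics, baseline adjustment adds 0.31 to 0.36 to the chance of detection at 30 per arm and 0.14 to 0.29 at 67. Those kinetics start every participant's decline on Day 1, so contacts caught before their natural peak are not represented. The result on medians rests on the assumed 4-to-7-day detectability. Severity is low because the analysis is exploratory and may not be run; it is best labelled a free improvement.

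**What to change.** In SAP 5.5.1.3, for contacts infected at baseline:

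1. Among those with detectable RNA at baseline (the population also admits NS1-only positives), report by arm the baseline log10 RNA together with either the log10 change from Day 1 predose at Days 5 and 9 or the post-baseline log10 peak adjusted for baseline log10 RNA. Step 3 favours the adjusted form, since a plain difference can lose its advantage near the detection limit. Keep the unadjusted peak as supportive.
2. Treat time to end of detectable RNA as interval-censored between the last detectable and the next undetectable sample, and report the proportion undetectable at Days 5 and 9 by arm, using the analysis windows in SAP Table 2.

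The cost is SAP wording and programming. No new samples, assays or visits are needed.

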1. INTRODUCTION

This statistical analysis plan (SAP) contains definitions of analysis sets, derived variables and statistical methods for the analysis of efficacy and safety of study drug JNJ-64281802. A separate document, the data presentation specifications (DPS), for mock shells and a table of contents for tables, figures and listings is also produced. The SAP is to be interpreted in conjunction with the protocol¹ (amendment 3).

The study was prematurely ended on 02 October 2024 when 21 laboratory confirmed dengue infections between baseline and last day of dosing (+1 day) were observed in the primary analysis population and 14 symptomatic dengue infection between baseline and last day of dosing (+1 day) were observed in the complete study population. This decision was taken by Johnson & Johnson based on portfolio reprioritization and was not based on any safety concerns. The current SAP will cover the final analysis (FA). Changes to the per protocol planned analysis are described in section 6.2, Appendix 2.

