A HHC is a person who lives, spends the night, or regularly attends/shares/consumes cooking/meals in the same dwelling or housing complex as the index case. A household can include one or more families, or community contacts in a single or in multiple houses or dwellings, depending on the country, site, social-economic, and cultural characteristics. Co-workers and acquaintances can also be considered HHCs, if they spend time together with the index case (eg, during early morning hours or twilight hours). HHCs had to be asymptomatic at screening and could include participants with no evidence of current DENV infection (consisting of naïve and historical DENV infected participants) or with evidence of current DENV infection as confirmed by laboratory assessments on samples taken at baseline.

Participants (ie. HHCs) were randomized in a 1:1:1 ratio to receive the study intervention as high dose regimen (HDR), low dose regimen (LDR), or as matching placebo in a double-dummy fashion. The study used randomization at the individual participant level. Participants were assigned to 1 of 3 intervention groups based on a computer-generated randomization schedule prepared before the study by or under the supervision of the sponsor. The randomization was balanced by using randomly permuted blocks and was stratified by country. A separate randomization list was created for the PK substudy.

- * Based on negative results for DENV RNA and NS1 protein assays
- ° Based on positive results for DENV RNA or NS1 protein assays

The interactive web response system (IWRS) assigned a unique intervention code, which dictated the intervention assignment and matching study intervention kit for the participant. The investigator will not be provided with randomization codes. The codes will be maintained within the IWRS, which has the functionality to allow the investigator to break the blind for an individual participant.

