The following exploratory analysis are left out:

- Exploratory analysis on the prophylactic effect of JNJ-64281802 with respect to the prevention of DENV infection as measured by DENV ribonucleic acid (RNA)
- Exploratory analysis on the prophylactic effect of JNJ-64281802 as measured through detection of DENV NS1 protein

It is clear from the available data that all laboratory confirmed DENV infections have detectable RNA on at least 1 time point, while only a minority have detectable DENV NS1 protein.

- Exploratory analysis to evaluate the prophylactic effect of JNJ-64281802 with respect to the prevention of symptomatic DENV infection up to Day 40, Day 50 and Day 90

Only isolated cases of symptomatic DENV infections after the last dose of study intervention are observed.

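### SAP 5.5.1.3 plans the mean and SD of peak DENV RNA with copies/mL as the only stated unit and no log10 scale or geometric mean; with few infections per arm these two statistics will probably be uninformative (minor, exploratory)

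*SAP*

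**What the plan says.** Section 5.5.1.3 of the SAP covers two populations: participants infected after a negative baseline, and participants already infected at baseline.

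- **Endpoint.** For the first population the peak is the "Maximum of all measured DENV RNA values". For the second it is the same maximum restricted to post-baseline values. Neither definition mentions a transformation.
- **Unit.** Table 5 is titled "Data Handling Rules for DENV RT-qPCR levels (copies/mL". It imputes 500 for detected values below the LLOQ and 1,100,000,000 for values above the ULOQ. Undetected target is set to 15, described as "LOD (from DENV-1)/2 rounded to the nearest integer".
- **Summary.** The plan is that "Descriptive statistics on peak of detectable DENV RNA will be calculated for each study intervention group separately". Which statistics are meant is then spelled out: "Statistics include sample size (n), mean, SD, median, minimum, and maximum". The same list is repeated for the post-baseline peak. The only transformation named in the section is the log-log method for the Kaplan-Meier confidence intervals.
- **Contrast.** SAP 5.7.1 does list a geometric mean for plasma concentrations.
- **Status.** SAP 1.1 puts both objectives among the exploratory analyses that may or may not be run, depending on the unblinded primary and secondary results, to generate hypotheses. No test is planned.

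**The concern.** Viral load that can range over several orders of magnitude is normally summarised on a log scale. On the copies/mL scale a mean adds up values that may differ a million-fold, so in a small group it mostly reports the largest value, and the SD does much the same. An analyst following the SAP as written would tabulate both statistics in copies/mL.

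Two things are at stake. A real reduction in viral load among breakthrough infections could be hidden or reversed in the means. In addition, if the drug prevents infections, the active arms will hold fewer cases than placebo. A larger group is more likely to contain an extreme value, so the raw placebo mean tends to be higher even when the drug has no effect on viral load.

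**Working it through.** **1. Table 5 reproduced.** 29/2 = 14.5, rounded to 15; 1000/2 = 500; 10^9 + 10^9/10 = 1.1 × 10^9. All three match the SAP.

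**2. Possible range.** SAP Appendix 2 reports that "all laboratory confirmed DENV infections have detectable RNA on at least 1 time point", so 500 is the floor for a breakthrough peak. 1.1 × 10^9 / 500 = 2.2 million-fold, or log10(2.2 × 10^6) = 6.34. For participants infected at baseline every post-baseline value may be undetected, so the floor there is 15 and the span is log10(1.1 × 10^9 / 15) = 7.87. These are assay limits, not observed spread.

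**3. Cases per arm.** SAP section 1 reports that "21 laboratory confirmed dengue infections between baseline and last day of dosing (+1 day) were observed in the primary analysis population", and participants were "randomized in a 1:1:1 ratio to receive the study intervention". An equal split is 7 per arm. Under the planning efficacy of 75% for the high dose, cases fall in the ratio placebo : HDR : LDR = 1 : 0.25 : (1 − PE of LDR):

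| PE of LDR | Placebo | HDR | LDR |
|---|---|---|---|
| 0% | 21/2.25 = 9.3 | 2.3 | 9.3 |
| 37.5% | 21/1.875 = 11.2 | 2.8 | 7.0 |
| 75% | 21/1.5 = 14.0 | 3.5 | 3.5 |

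The documents do not give the number infected at baseline.

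**4. What one value can do.** Seven cases, six at 10^6 and one at 1.1 × 10^9:
- raw mean = 1.106 × 10^9 / 7 = 1.58 × 10^8
- median = 10^6
- geometric mean = 10^((6 × 6 + 9.04)/7) = 2.7 × 10^6
- share of the sum from the single value = 1.1/1.106 = 99.5%

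This is not inevitable. With six at 5 × 10^8 and one at 1.1 × 10^9, the share is 1.1/4.1 = 27%.

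**5. Simulation.** The documents give no SD for log10 peak RNA. I assumed normal log10 peaks centred at 6, SD 0.5 to 2.0, with the Table 5 limits applied. The reduced arm is centred at 5 in the wrong-order rows, which have 5 infected per arm. Figures carry about one percentage point of simulation and rounding error.

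| Assumed log10 SD | 0.5 | 1.0 | 1.5 | 2.0 |
|---|---|---|---|---|
| Largest value's median share of the arm's sum, n = 5 | 47% | 68% | 81% | 86% |
| Wrong order, raw mean | <1% | 12% | 22% | 29% |
| Wrong order, planned median | <1% | 9% | 19% | 25% |
| Wrong order, log10 mean | <1% | 6% | 15% | 22% |
| No true difference, 12 vs 3 cases: raw mean lower in the smaller arm | 60% | 66% | 69% | 66% |
| The same, log10 mean | 50% | 50% | 50% | 50% |

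The log10 row can be checked by hand. Ignoring the assay limits, the chance of wrong order is Φ(−1/(SD × √(2/5))), which gives 0.1, 6, 15 and 21%.

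In the 12 versus 3 comparison the raw placebo mean is more than 10-fold higher in 21, 37 and 40% of trials at SD 1.0, 1.5 and 2.0. The geometric mean is more than 10-fold higher in about 6, 14 and 20%. At SD 0.5 both are under 1%.

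**The case against.** Four points on the other side have weight.

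- **The mean and SD are not the whole summary.** The median, minimum and maximum are planned as well. They pass through a log transform unchanged, except that with an even number of cases the raw median averages two values. The planned median recovers part of the loss, and much of the remaining misordering is small-sample noise that the log10 mean also carries. This stands.
- **The analysis scale is inferred.** Copies/mL is the unit for handling and imputation, and imputing on that scale is compatible with a later log10 step. The table shells are in separate data presentation specifications that are not among the documents. So the accurate statement is that no transformation is stated, not that none will be used. This stands, and the ambiguity calls for the same one-line remedy.
- **Dominance by one value depends on the spread.** A reader might infer that one participant decides every arm's mean. The documents do not support that: they give no spread, the share falls to about half at SD 0.5, and the example above with a 27% share is possible.
- **Little hangs on it.** The analysis is conditional, descriptive and untested, and nothing in the SAP ranks the arms by mean. The wrong-order rates therefore show how informative each statistic is; they are not error rates of a planned inference. For early treatment, time to end of detectable RNA and signs and symptoms are also planned, and neither depends on the copies/mL scale.

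What remains is that two of the listed statistics are a poor choice on the only unit the SAP states, and that the SAP uses a geometric mean elsewhere.

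**Conclusion.** The point holds as a minor one. The SAP names no log scale for peak DENV RNA, and a mean and SD in copies/mL from a handful of cases per arm will probably be driven by the largest value. At an assumed log10 SD of 1.0 to 2.0 with 5 cases per arm, the raw mean misorders the arms about 6 to 7 percentage points more often than the log10 mean, and about 3 to 4 points more often than the planned median. With 12 versus 3 cases and no effect, it favours the smaller arm in about two thirds of trials. At SD 0.5 the misordering almost vanishes, though the tilt towards the smaller arm remains at 60%. All these figures rest on assumed normality on the log10 scale, the assumed SD and the assumed numbers per arm.

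A reader might go further and infer that the plan offers no usable summary of viral load, or that the efficacy conclusion is affected. Neither follows: the median and range are planned, and the primary and key secondary endpoints are binary and do not use RNA quantity.

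**What to change.** State in SAP 5.5.1.3 and in the table shells that peak and post-baseline peak DENV RNA are analysed as log10 copies/mL. Log-transform the Table 5 imputed values as well: 15, 500 and 1.1 × 10^9 become 1.18, 2.70 and 9.04. Report by arm n, mean and SD of log10, geometric mean, median, minimum and maximum.

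The cost is one line of SAP text and one line of code, with no new data. Because the decision to run this analysis follows the unblinded results, the scale is best fixed before unblinding. If that has passed, label the log10 summary as added afterwards and show it beside the planned one.
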